## 3. PURPOSE AND SCOPE

COPD is a leading cause of morbidity and mortality throughout the world. The role of ICS in COPD has been debated for decades and studies have been conducted to investigate the effect

of ICS-containing therapy in patients with COPD. The aim of this real world study is to assess effectiveness and safety profile between inhaled tiotropium/olodaterol (Tio/Olo) and corticosteroids / long-acting  $\beta$ 2-agonists (CS/LABA).

## **4. AMENDMENTS AND UPDATES**

None

## **5. RESEARCH QUESTION AND OBJECTIVE**

**Primary objective:**

- To compare time to the first moderate or severe COPD exacerbations between initiators of Tio/Olo and ICS/LABA after entry between 1st January 2014 and 31st December 2019

**Secondary objectives:**

- To compare time to escalation to triple therapy between initiators of Tio/Olo and ICS/LABA;
- To compare the rate of escalation to triple therapy between initiators of Tio/Olo and ICS/LABA;
- To compare the time to first hospitalization for community-acquired pneumonia between initiators of Tio/Olo and ICS/LABA;
- To compare the number of prescriptions of rescue medication between initiators of Tio/Olo and ICS/LABA
- To compare the annualized rate of moderate or severe COPD exacerbation

The study period between 1st January 2014 and 31st December 2019 apply to secondary objectives above.

## **6. RESEARCH METHODS**

### **6.1 STUDY DESIGN**

This study will be a non-interventional cohort study using Taiwan National Health Insurance (NHI) claims database, Taiwan Cancer Registry (TCR) and Taiwan Mortality Data. It is a secondary health data environment with relevant information on treatment and disease outcomes of COPD patients among a population of predominantly ethnic Han Chinese. As a publicly funded single payor health insurance program, a wide range health services, including hospital care, emergency visits, ambulatory clinic services, and prescription drugs are covered for virtually all Taiwan residents. The complete capture of health care encounters reimbursed by NHI among a defined group of patients has served as the basis of many longitudinal studies that evaluated safety profiles of prescribed medications.

Health data that are available for research are provided by the Health and Welfare Data Science Center (HWDSC) of the Department of Statistics, Ministry of Health and Welfare. The HWDSC staff encrypt the national ID for all individuals according to a secure encryption algorithm that is specific for each study, and the encrypted ID all individuals is used for linkage between databases. While the study will provide safety data on drugs of interest, from a regulatory perspective the source data are not auditible, nor de-identified individual level data be brought outside of HWDSC for independent verification of analysis.

Limitations of health insurance databases are well-known, as there is no information on results of clinical parameters (such as blood pressure and body mass index), clinical examinations (such as spirometry findings), or life style attributes (such as smoking). A specific items that needs to be considered for this particular study project is whether the findings are generalizable to COPD patients in China. While there is high similarity between COPD patients in Taiwan and those in China in terms of ethnicity and dietary patterns, management patterns for COPD patients, including comorbid conditions, concomitant medications, and use of traditional Chinese medication regimens, may be different.

Taking into account the strengths and potential limitations of the data source, the population-based nature and potentially large study size of patients on drugs of interest are the major reasons that this data source is a viable option for the study.

## **6.2 SETTING**

Incident Tio/Olo combined inhaler or a ICS/LABA combined inhaler use would be identified from the Taiwan National Health Insurance (NHI) claims data through 2014 to 2019, with a 1-year look-back period to define new user.

## **6.3 STUDY POPULATION**

### **Inclusion Criteria:**

1. At least one prescription for Tio/Olo combined inhaler or a LABA/ICS combined inhaler between 1st January 2014 and 31st December 2019.
  - a) The first dispensing of either Tio/Olo or LABA/ICS combined inhaler will be defined as the index date;
  - b) For the main analyses, only fixed dose combination (FDC) inhalers will be included.
2. Aged  $\geq$  40 years on the index date
3. At least one diagnosis of COPD (ICD9: 491.x, 492.x, 496; ICD10: J41.x, J42, J43.x, J44.x) at any time prior to or on the index date;

[figure not shown]
4. At least one year of continuous medical and health insurance plan prior to the index date will be required to allow for a look-back period for the covariates and identification of new use of the study drugs;
5. At least one record in the health insurance system database.

**Exclusion Criteria:**

1. Any use of LAMA/LABA, ICS/LABA, or ICS/LAMA/LABA in free or fixed form for one year prior to the index date (the free combination will be defined as the prescriptions of the interest products within 30 days of each other);
2. Individuals with asthma, allergic rhinitis, lung cancer, interstitial lung disease, or lung transplant identified at any time prior to the index date [REDACTED]; [REDACTED];

Relevant ICD codes and procedure code are provided in the Annex.

Figure 1. Patient selection flow chart

## **6.4 STUDY VISITS**

Not applicable.

## **7. VARIABLES**

### **7.1 EXPOSURES**

Exposure of this study is defined as new initiation of Tio/Olo or ICS/LABA (FDC) during the study period. Detailed drug codes are provided in the Annex.

### **7.2 OUTCOMES**

#### **7.2.1 Primary outcomes**

##### **➤ Time to the first moderate or severe COPD exacerbations after index date**

The definition of moderate or severe COPD exacerbation:

- a. Moderate exacerbations will be defined as an outpatient visit with a diagnosis code for COPD in any field + a prescription for an oral corticosteroid or an antibiotic for respiratory infections
- b. Severe exacerbations will be defined as a hospitalization or emergency room visit with a primary diagnosis for COPD

Detailed diagnosis codes are listed in Annex.

Tio/Olo users will be matched to the comparator through 1:1 propensity score matching. For the analysis of the primary outcome, individuals will be followed up from the index date until the first moderate or severe COPD exacerbation. For detailed, please refer to section [10.1](#). As time-to-event data, the main analysis will be univariate proportional hazard regression analysis to estimate the hazard ratio (Tio/Olo vs. comparator) and its 95% confidence interval (CI). Detailed analytic approach is described in Section [10.1](#).

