7. RATIONALE AND BACKGROUND

COPD is a leading cause of morbidity and mortality throughout the world. Long-acting bronchodilator medications, which include long-acting β2-agonists (LABAs) and the long-acting muscarinic antagonists (LAMAs) such as tiotropium, are the central maintenance therapy to the management of COPD, with inhaled corticosteroids (ICSs) added with increasing severity. The up-to-date GOLD guideline recommends to initiate ICS/LABA in patients with high blood eosinophils level and frequent exacerbation history[P21-01394]. However, ICS containing therapy has been widely used inappropriately in real world practice.

The role of ICS in COPD has been debated for decades and studies have been conducted to investigate the effect of ICS-containing therapy in patients with COPD. INSPIRE [P07-11820] study indicated that ICS/LABA and tiotropium showed similar effects on the reduction of exacerbations, while the risk of pneumonia was higher in the ICS/LABA group. And the FLAME [P16-05628] study showed LAMA/LABA was superior to ICS/LABA in terms of exacerbation prevention, while in some newly published data focusing on FDC triple therapy showing reversed results.

With more and more fixed dose combination medications, i.e. LAMA/LABA, ICS/LABA/LAMA, approved and prescribed in recent years, it is of clinical interests to understand the effectiveness and safety profile of these therapies in real world settings.

The aim of this real world study is to assess effectiveness and safety profile between tiotropium/olodaterol (Tio/Olo) and ICS/LABA. The primary outcome of the study will be time to first moderate or severe COPD exacerbations. Other outcomes include time to ICS/LABA/LAMA escalation, rate of escalation to triple therapy, pneumonia and rescue medication use.

NIS Protocol Page 22 of 48 BI Study Number: 1237-0110 c38660249-01

Proprietary confidential information © 2022 Boehringer Ingelheim International GmbH or one or more of its affiliated

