### **(3). Time to first hospitalization for community-acquired pneumonia after entry**

Community-acquired pneumonia related diagnosis codes and operational definition are listed in the Annex.

As time-to-event data, the analysis will be univariate proportional hazard regression analysis to estimate the hazard ratio (Tio/Olo vs. comparator) and its 95% confidence interval (CI).

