### **(5). Annualized rate of moderate or severe COPD exacerbation after the index date**

The definition of moderate or severe COPD exacerbation:

- a. Moderate exacerbations will be defined as an outpatient visit with a diagnosis code for COPD in any field + a prescription for an oral corticosteroid or an antibiotic for respiratory infections, prescriptions within 30 days of each other were considered as continuation of the initial exacerbation.
- b. Severe exacerbations will be defined as a hospitalization or emergency room visit with a primary diagnosis for COPD; hospitalizations or emergency room visits within 30 days of each other were considered as continuation of the initial exacerbation.

For annualized rates, it will be calculated for each cohort as follows:

Annualized rate among the Tio+Olo cohort = (total number of events in the Tio+Olo cohort during the given time period) / (total person-year at risk from current use of Tio+Olo during the given period)

Annualized rate among the comparison cohort = (total number of events in the comparator LABA/ICS cohort during the given time period) / (total person-year at risk from current use of comparator LABA/ICS during the given period)

For annualized rate of moderate or severe COPD exacerbations, the rate ratio of Tio+Olo – exposed group relative to LABA/ICS group, along with 95% CI will be derived using negative binomial model.

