## Appendix 5. Drugs of interest

Groups	ATC code
Use of other respiratory drugs	
Mucolytics	R05CB, R05CB01, R05CB02, R05CB03, R05CB04, R05CB05, R05CB06, R05CB10, R05CB11, R05CB91, R05CB92
Theophylline	R03DA04, R03DA54, R03DA74, R03DB04
SABA	R03AC02, R03AC03, R03AC04, R03AC06
SAMA	R03BB01
SABA/SAMA	R03AL01, R03AL02
Drugs for COPD exacerbation treatment	
Oral corticosteroid	H02AB01, H02AB02, H02AB04, H02AB05, H02AB06, H02AB08, H02AB10, H02BX, H02BX91
Antibiotic for COPD exacerbation	J01AA02, J01CA04, J01CR02, J01CR05, J01EE01, J01DC01, J01DC02, J01DC03, J01DC04, J01DC05, J01DC06, J01DC07, J01DC09, J01DC14, J01DD01, J01DD02, J01DD04, J01DD05, J01DD06, J01DD07, J01DD08, J01DD12, J01DD13, J01DD14, J01DD52, J01DD62, J01DE01, J01DE02, J01FA01, J01EA02, J01EA03, J01EA06, J01EA07, J01EA08, J01FA09, J01FA10, J01FA15, J01FA91, J01MA01, J01MA02, J01MA03, J01MA04, J01MA06, J01MA07, J01MA09, J01MA12, J01MA14, J01MA15
Drugs for Medication history	

 
● Cardiovascular drugs
 
	
Anti-hypertensives	C02AA01, C02AA02, C02AA04, C02AB01, C02AB02, C02AC01, C02CA01, C02CA04, C02CA, C02CC02, C02DA01, C02DB02, C02DC01, C02DD01, C02LA01, C02LA50, C02LA51, C02LB01, C02LG02, C02N, C03AA01, C03AA03, C03AA06, C03AA07, C03AA, C03BA04, C03BA08, C03BA11, C03CA01, C03CA02, C03CA04, C03CC01, C03DA01, C03DA04, C03DB01, C03DB02, C03EA01, C03EA, C07AA01, C07AA02, C07AA03, C07AA05, C07AA06, C07AA07, C07AA12, C07AA15, C07AA19, C07AB02, C07AB03, C07AB04, C07AB05, C07AB07, C07AB09, C07AB12,

	C07AG01, C07AG02, C07BA68, C07BB02, C07CA03, C07CB03, C07DA06, C08CA01, C08CA02, C08CA03, C08CA04, C08CA05, C08CA07, C08CA08, C08CA09, C08CA12, C08CA13, C08CA15, C08DA01, C08DB01, C09AA01, C09AA02, C09AA03, C09AA04, C09AA05, C09AA06, C09AA07, C09AA08, C09AA09, C09AA16, C09BA01, C09BA02, C09BA04, C09BB04, C09BB05, C09BB, C09BB, C09CA01, C09CA02, C09CA03, C09CA04, C09CA06, C09CA07, C09CA08, C09CA09, C09DA01, C09DA03, C09DA04, C09DA06, C09DA07, C09DA08, C09DA09, C09DB01, C09DB02, C09DB04, C09DB07, C09DX01, C09DX03, C09DX04, C09XA02, C09XA52, C09XA53, C09XA54
Antiarrhythmics	C01AA04, C01AA05, C01AA07, C01AA08, C01AB01, C01AC01, C01BA01, C01BA02, C01BA03, C01BA04, C01BA08, C01BB01, C01BB02, C01BC03, C01BC04, C01BD01, C01BD07, C01CA02, C01CA04, C01CA06, C01EB10, C01EB17, C07AA01, C07AA02, C07AA03, C07AA05, C07AA07, C07AA12, C07AA15, C07AA19, C07AB02, C07AB03, C07AB04, C07AB05, C07AB07, C07AB09, C07AB12, C08DA01, C08DB01

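### The moderate-exacerbation rule counts antibiotic-treated outpatient pneumonia with a secondary COPD code as a primary event, which may bias the hazard ratio toward Tio/Olo

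*SAP*

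**What the plan says.** SAP 7.2.1 gives two routes to the primary event.

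- Moderate: "an outpatient visit with a diagnosis code for COPD in any field + a prescription for an oral corticosteroid or an antibiotic", the antibiotic being one for respiratory infections.
- Severe: "Severe exacerbations will be defined as a hospitalization or emergency room visit with a primary diagnosis for COPD".

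SAP 7.2.2(5) uses the same moderate rule for the annualised exacerbation rate, adding only a 30-day merging rule. SAP Appendix 5 identifies the qualifying antibiotics by ATC code under the label "Antibiotic for COPD exacerbation"; the list is not tied to an indication.

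Pneumonia is a separate secondary outcome in SAP 7.2.2(3), but only as a first hospitalisation for community-acquired pneumonia. Protocol section 7 says of the cited trial of ICS/LABA against tiotropium that "the risk of pneumonia was higher in the ICS/LABA group". It gives no ratio.

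SAP Table 2 reports hazard ratios for moderate, severe and all exacerbations separately, and Table 6 does the same for annualised rates. Protocol 9.9 acknowledges misclassification of study variables in general terms and does not name pneumonia.

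**The concern.** Consider an outpatient visit with pneumonia as the main diagnosis, COPD as a secondary code and a listed antibiotic. Every element of the moderate rule is met, so the visit is a primary event. The respiratory-infection qualifier does not help, because pneumonia is a respiratory infection. All cohort members have a COPD diagnosis by inclusion, so a secondary COPD code at such a visit is plausible.

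If outpatient pneumonia is commoner on ICS/LABA, these visits are scored against ICS/LABA on effectiveness whether or not the two treatments differ in preventing exacerbations. Propensity-score matching balances baseline characteristics and does not correct misclassification of outcomes after the index date. At stake is whether a hazard ratio below 1 can be read as fewer exacerbations, or partly reflects fewer pneumonias.

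**Working it through.** **What each route admits**

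| Event | Diagnosis position required | Pneumonia visit with secondary COPD code |
|---|---|---|
| Moderate (outpatient) | COPD in any field | Counts, if a listed antibiotic is prescribed |
| Severe (admission or ER) | COPD primary | Does not count |
| Pneumonia outcome | Hospitalisation only | Outpatient visit never counts |

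**Inputs**

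- From Protocol 9.5: planning hazard ratio 0.90, two-sided alpha 0.05, 90% power, cited trial hazard ratio 0.78.
- Assumed, because the documents give neither: *p*, outpatient-pneumonia events as a fraction of true exacerbation events in the ICS/LABA arm; and *r*, the rate ratio of those events, Tio/Olo vs ICS/LABA.
- *H* is the true exacerbation hazard ratio.

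The plan has no figure of its own for this overlap, so there is none to reproduce. The stated sample size of 4,978 is not used below.

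**Formula.** Scale the ICS/LABA exacerbation hazard to 1. The observed hazard is 1 + *p* on ICS/LABA and *H* + *rp* on Tio/Olo, so

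apparent HR = (*H* + *rp*) / (1 + *p*).

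**Direction.** The apparent HR is below *H* only when *H* + *rp* < *H* + *Hp*, that is, when *r* < *H*. The break-even values of *r* are therefore 1.00 with no true effect, 0.90 at the planning value and 0.78 at the cited value.

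**Size with *H* = 1.00**

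| *p* | *r* = 0.8 | *r* = 0.6 | *r* = 0.5 |
|---|---|---|---|
| 5% | 0.990 | 0.981 | 0.976 |
| 10% | 0.982 | 0.964 | 0.955 |
| 15% | 0.974 | 0.948 | 0.935 |

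For example, *p* = 10% and *r* = 0.6 give (1 + 0.06) / 1.10 = 0.964.

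**A case that goes the other way.** With *H* = 0.78, *p* = 10% and *r* = 0.8, the apparent HR is (0.78 + 0.08) / 1.10 = 0.782. The shift is slightly toward 1, against Tio/Olo.

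**Effect on false positives with *H* = 1.00.** The events implied by the planning inputs are 4(1.96 + 1.2816)² / (ln 0.9)² = 3,786, so SE(log HR) = 2/√3,786 = 0.0325. The chance of a significant result favouring Tio/Olo is Φ(−1.96 − ln(apparent HR)/0.0325), nominally 2.5%. At *r* = 0.6 it is 8.6% for *p* = 5%, 21% for *p* = 10% and 38% for *p* = 15%. These figures hold the event count at the planning value. The count left after matching and on-treatment censoring is not stated; fewer events would make the inflation smaller and more events would make it larger.

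**The case against.** The evidence for a difference between arms is indirect. The background statement compares ICS/LABA with tiotropium, not with Tio/Olo, gives no figure and does not mention outpatient pneumonia. Both *p* and *r* are assumed, and at *p* = 5% the shift from 1.00 is only 0.010 to 0.024, against a planning effect of 0.10. This stands: it limits what can be said about direction and size, but does not close the gap in the definition.

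A reader might infer that the rule necessarily biases the hazard ratio toward Tio/Olo. The documents do not support that, since it requires *r* < *H* and no value of *r* is given.

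A reader might also infer that the pneumonia outcome loses these events. It does not. That outcome is hospitalisation only, so outpatient pneumonia was never part of it. A moderate exacerbation is not among the censoring events for it in SAP 10.1, so a patient treated as an outpatient and later admitted while still on the index drug is counted.

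Tables 2 and 6 offer a partial check. The severe component is guarded by the primary-diagnosis requirement, so a gap between the moderate and severe estimates would be visible, but it would not be specific to pneumonia.

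Parts of the SAP are redacted, including material between 10.1 and 10.3, so a sensitivity analysis on this point may exist. It would leave the main definition in 7.2.1 as it is.

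Finally, replacing the primary definition would be debatable. Dropping pneumonia-coded visits also drops genuine exacerbations with concurrent pneumonia, possibly more often on ICS/LABA, which pushes the other way. Changing the matching baseline covariate would depart from Protocol 9.3.3 and alter the propensity score. That argues for an added analysis and against a substituted definition.

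**Conclusion.** The overlap is plain from the text: the moderate rule admits antibiotic-treated outpatient pneumonia when COPD is also coded, and nothing visible guards against it as the primary-diagnosis requirement does for severe events. It affects the primary hazard ratio and the annualised exacerbation rate ratio.

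The bias toward Tio/Olo is possible, not established. Over the assumed ranges a true hazard ratio of 1.00 would appear as 0.990 to 0.935. The result rests on assumed *p* and *r*, and on the pneumonia excess reported against tiotropium carrying over to Tio/Olo and to outpatient cases. Even a small shift can matter if event numbers are near the planning value, so the point should be addressed before the data are analysed.

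**What to change.** Keep the definition in SAP 7.2.1 and 7.2.2(5), and the baseline exacerbation covariate in SAP 7.3, unchanged. Add to SAP 10.1:

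- A pre-specified analysis of the primary hazard ratio and the annualised exacerbation rate ratio in which an outpatient visit with a pneumonia code does not qualify as a moderate exacerbation on the antibiotic criterion alone. A visit with an oral corticosteroid still qualifies. The codes are those already in Appendix 4: ICD-9 480-486, 487.0; ICD-10 J10.0, J11.0, J12-J18.
- The number of first events reclassified, by arm. This shows directly how large the overlap is.
- A statement that a conclusion favouring Tio/Olo must be read alongside this analysis.

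The cost is SAP wording, one filter on codes already listed and extra rows in Tables 2 and 6. The added analysis drops some genuine exacerbations with concurrent pneumonia, possibly more often on ICS/LABA, so the two results should be read together.

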#### **7.2.2 Secondary outcomes**

Analysis of the secondary outcomes will be applied to the propensity-score matched cohorts developed for the primary outcome of interest. Detailed description of the analysis approach is described in Section [10.1](#)

### **(1). Time to triple therapy escalation after index date**

Triple therapy escalation, defined as any LAMA/LABA/ICS fixed dose combination or any concurrent use for 30 consecutive days of the following:

- a. any LAMA/LABA fixed dose combination + any ICS single formulation
- b. any LAMA single formulation + any LABA/ICS fixed dose combination
- c. any LAMA single formulation + any LABA single formulation + any ICS single formulation

The event date will be the 30th day after initiation of triple therapy.

As time-to-event data, the analysis will be univariate proportional hazard regression analysis to estimate the hazard ratio (Tio/Olo vs. comparator) and its 95% CI.

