9.2.2 Study population

Inclusion criteria:

- At least oneprescriptions for Tio/Olo combined inhaler or a LABA/ICS combined inhaler between 1st January 2014 and 31st December 2019.
 - a) The first dispensing of either Tio/Olo or LABA/ICS combined inhaler will be defined as the index date;
 - b) For the main analyses, only fixed dose combination (FDC) inhalers will be included.
- 2. Aged \geq 40 years on the index date
- 3. At least one diagnosis of COPD at any time prior to or on the index date;
- At least one year of continuous medical and health insurance plan prior to the index date will be required to allow for a look-back period for the covariates and identification of new use of the study drugs;
- 5. At least one record in the health insurance system database;

Exclusion criteria:

- 1. Any use of Tio/Olo, ICS/LABA, or ICS/LAMA/LABA in free or fixed form for one year prior to the index date;
- Individuals with asthma, allergic rhinitis, lung cancer, interstitial lung disease, or lung transplant identified at any time prior to the index date

NIS Protocol Page 24 of 48 BI Study Number: 1237-0110 c38660249-01

Proprietary confidential information © 2022 Boehringer Ingelheim International GmbH or one or more of its affiliated

For the analysis of the primary outcome, individuals will be followed up from the index date until the earliest of the date of: the follows, whichever first 1) moderate or severe COPD exacerbation; 2) disenrollment; 3) the end of the study period; 4) death; 5) discontinuation of the index drug use as a lapse of 1.5 months without subsequent prescription (except for switching from the index ICS/LABA to a different ICS/LABA); 6) adding ICS mono on top of Tio/Olo, or adding LAMA momo on top of the index ICS/LABA

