### **(2). Incidence rate of triple therapy initiation (first event per patient)**

Triple therapy escalation, defined as any LAMA/LABA/ICS fixed dose combination or any concurrent use for 30 consecutive days of the following:

- a. any LAMA/LABA fixed dose combination + any ICS single formulation
- b. any LAMA single formulation + any LABA/ICS fixed dose combination
- c. any LAMA single formulation + any LABA single formulation + any ICS single formulation

For incidence rates, it will be calculated for each cohort as follows:

Incidence rate among the Tio+Olo cohort = (total number of patients in the Tio+Olo cohort experiencing an event of interest for the first time during the given time period) / (total person-time at risk from current use of Tio+Olo during the given period)

Incidence rate among the comparison cohort = (total number of patients in the comparator LABA/ICS cohort experiencing an event of interest for the first time during the given time period) / (total person-time at risk from current use of comparator LABA/ICS during the given period)

The incidence rate ratio (IRR) and incidence difference for the outcome in the Tio+Olo - exposed group relative to that in the comparator group will be derived as follows:

Incidence rate ratio = incidence rate from the Tio+Olo cohort divided by the incidence rate from the matched comparator cohort.

Incidence difference = incidence rate from the Tio+Olo cohort – incidence rate from the matched comparator cohort

The IRR and their 95% CIs will be calculated using univariate negative binomial model. Incidence differences and their 95% confidence intervals will also be derived.

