Note that per study protocol, switching from one ICS/LABA to another ICS/LABA is not a censoring event.

Univariate proportional hazard regression model will be used to compare the time to event between the two treatment groups. It will provide an estimate of the hazard ratio (HR) of time to the first moderate or severe COPD exacerbation associated with Tio+Olo use relative to LABA/ICS use, along with 95% CI. In the event that there are baseline covariates with unequal distribution between the treatment groups, defined as absolute standardized difference larger than 0.1, the covariate(s) will be included in a multiple regression model in addition to the exposure status (Tio/Olo or LABA/ICS).

The analysis of the secondary objectives related to time to triple therapy escalation and time to first hospitalization for community-acquired pneumonia will be univariate proportional hazard regression model with an as-treated approach, similar to that of the primary analysis. The estimate of hazard ratio (HR) of time to triple therapy escalation and first hospitalization for community-acquired pneumonia associated with Tio+Olo use relative to LABA/ICS use,

[figure not shown]
Proprietary confidential information © 2022 Boehringer Ingelheim International GmbH or one or more of its affiliated companies

along with 95% CI will be provided. For the analysis of these time-to-event outcomes, patients will be followed until the event of interest or earliest of the date of the follows, whichever happened first:

- 1) outcome event of interest;
- 2) disenrollment;
- 3) the end of the study period;
- 4) death;
- 5) discontinuation of index drug use (a lapse of 45 days without subsequent prescription)
- 6) switching from Tio/Olo to ICS/LABA or from ICS/LABA to Tio/Olo

In the event that there are baseline covariates with unequal distribution between the treatment groups, defined as absolute standardized difference larger than 0.1, the covariate(s) will be included in a multiple regression model in addition to the exposure status (Tio/Olo or LABA/ICS).

[figure not shown]
Proprietary confidential information © 2022 Boehringer Ingelheim International GmbH or one or more of its affiliated companies

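### The definition of triple therapy escalation omits a LAMA/LABA inhaler used together with an ICS/LABA inhaler, so combining the two arms' inhalers is not itself an escalation event

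*SAP*

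**What the plan says.** SAP 7.2.2 (1) opens the event definition with "Triple therapy escalation, defined as any LAMA/LABA/ICS fixed dose combination or any concurrent use for 30 consecutive days of the following". Three mixes then follow:

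- (a) "any LAMA/LABA fixed dose combination + any ICS single formulation"
- (b) a single-agent LAMA inhaler with an ICS/LABA fixed-dose inhaler
- (c) three single-agent inhalers, one from each class

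The event is dated to the 30th day after triple therapy starts. SAP 7.2.2 (2), the incidence rate of triple therapy initiation, repeats the same list.

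For the secondary time-to-event outcomes, SAP 10.1 ends follow-up at, among other things, a 45-day gap in index-drug prescriptions and, as a separate item, "switching from Tio/Olo to ICS/LABA or from ICS/LABA to Tio/Olo". It does not say how adding the other arm's inhaler is told apart from switching to it.

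Two other places describe triple therapy differently. The primary censoring rule (SAP 10.1 item 6, and likewise Protocol 9.7.1) refers to free or fixed combinations of the three classes, with no list of permitted mixes. Protocol 9.2.2, item 6 of the primary follow-up rules, instead names only single-agent additions: "adding ICS mono on top of Tio/Olo, or adding LAMA momo on top of the index ICS/LABA".

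**The concern.** The outcome is meant to capture a patient's move to LAMA, LABA and ICS together. The missing regimen does that using the two products the study compares. A Tio/Olo patient who continues Tio/Olo and adds an ICS/LABA inhaler, or an ICS/LABA patient who adds a LAMA/LABA inhaler, has reached all three classes, yet the written definition records no event.

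Both escalation outcomes use the same list, so the hazard ratio, the incidence rate ratio and the incidence difference share the gap. The text also leaves room for different programming: one analyst may treat the added inhaler as a switch, another may leave the patient at risk, and a third may count an escalation by borrowing the broader wording of the primary censoring rule.

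**Working it through.** The plan states no figure on this point, so there is none to reproduce. The check is logical, followed by an illustration of size.

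**Step 1. Which mixes can supply all three classes?** SAP Appendix 3 lists single LAMA, single LABA, single ICS, ICS/LABA, LABA/LAMA and triple products. The combinations that cover all three classes with no redundant product are:

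| Mix | In the SAP list? |
|---|---|
| Triple fixed-dose inhaler | Yes, opening sentence |
| LAMA/LABA + single ICS | Yes, (a) |
| ICS/LABA + single LAMA | Yes, (b) |
| Single LAMA + single LABA + single ICS | Yes, (c) |
| LAMA/LABA + ICS/LABA | No |

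Four of the five are listed. The fifth fails (a) because its ICS is not a single formulation, fails (b) because its LAMA is not, and fails (c) because neither product is a single agent. The list has no wording such as 'for example', so it is closed.

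**Step 2. Does another rule count the patient?**

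- *Addition read as a switch.* The patient is censored when the other arm's inhaler starts. Because the event date is day 30, a switch rule applied at first dispensing would act before the event even if the mix were listed.
- *Addition not read as a switch.* The 45-day lapse is not triggered while the index inhaler continues to be dispensed. The patient stays at risk, event-free, and adds index-drug person-time to the denominator.
- *ICS/LABA patient adding a LAMA/LABA product other than Tio/Olo.* Appendix 3 lists two such products. The switch rule names only Tio/Olo, so on its face this patient stays at risk.

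None of these records an escalation. A patient who remains in follow-up and later reaches a listed regimen is counted then, at a later date.

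**Step 3. Size, under assumed shares.** Let qT and qI be the shares of escalations by the missing route in the Tio/Olo and ICS/LABA arms. If those events are lost and person-time is little changed:

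- observed rate = true rate × (1 − q) in each arm
- observed ratio = true ratio × (1 − qT)/(1 − qI)

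| qT | qI | Factor on the ratio |
|---|---|---|
| 0% | 0% | 1.00 |
| 10% | 0% | 0.90/1.00 = 0.90 |
| 10% | 5% | 0.90/0.95 = 0.947 |
| 20% | 5% | 0.80/0.95 = 0.842 |
| 10% | 10% | 0.90/0.90 = 1.00 |
| 5% | 10% | 0.95/0.90 = 1.056 |
| 0% | 10% | 1.00/0.90 = 1.111 |

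With equal shares of 10%, the ratio is unchanged, but both rates, and therefore the incidence difference, fall to 0.90 of their true values. All shares here are assumptions; the documents supply none. Late counting of some patients would shrink the loss.

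**The case against.** The strongest defence is that the omission may be deliberate. In dispensing data, an ICS/LABA fill during remaining Tio/Olo supply can look the same as a switch. The SAP has a switch rule, and the missing mix contains two LABA products, so treating cross-arm fills as switches would be coherent. What stands is the risk of miscounting switchers with leftover supply. It does not justify the gap: the SAP does not say the omission is intended, the 30-day concurrent-use requirement already screens out short overlaps, and a continued index refill separates most true additions from switches.

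Several stronger readings are tempting but not supported:

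- *That the gap favours Tio/Olo.* A reader might infer that Tio/Olo patients take this route more often because single ICS is their only listed add-on. But each arm has exactly one listed single-agent add-on (ICS for Tio/Olo, LAMA for ICS/LABA), and Protocol 9.2.2 names both.
- *That these patients can never be counted.* Only the regimen itself is not an event; later counting remains possible.
- *That the primary analysis keeps ICS-exposed time in the Tio/Olo arm.* SAP 10.1 item 6 on its face already censors a free combination of the three classes. The time would stay only if that item were narrowed to the 7.2.2 list or to Protocol 9.2.2 and the addition were also not read as a switch.
- *That baseline and outcome use conflicting concepts.* The exclusion rule in SAP 6.3 ("the free combination will be defined as the prescriptions of the interest products within 30 days of each other") removes any prior LAMA/LABA or ICS/LABA use in the look-back year, so a patient on both inhalers is excluded however triple therapy is defined.

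The two affected outcomes also summarise the same first event, so they are not two independent losses.

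**Conclusion.** The concern holds as a gap in definition. Followed as written, the SAP does not count concurrent LAMA/LABA and ICS/LABA inhalers as escalation, although all three classes are in use. The list is also narrower than the SAP's own primary censoring wording, while Protocol 9.2.2 gives a third description.

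Any use of the route lowers the escalation rates. The hazard ratio and rate ratio are distorted only if its use differs by arm. Size and direction are unknown: a 10-point imbalance with no use in the other arm gives a factor of 0.90 or 1.11, equal use gives 1.00, and negligible use in both arms is equally compatible with the documents. The conclusion rests on reading the list as closed, which its wording requires, and on the visible SAP text, where both outcome definitions are complete. It should be settled before analysis because the outcome cannot be programmed unambiguously otherwise.

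**What to change.** - In SAP 7.2.2 (1) and (2), add a fourth mix (d): any LAMA/LABA fixed-dose inhaler with any ICS/LABA fixed-dose inhaler, under the same 30-consecutive-day rule.
- For (d), require at least one further dispensing of the index drug after the added inhaler starts, so that leftover supply at a true switch is not counted. State the time window for that dispensing.
- In SAP 10.1, apply the escalation test before the switch rule, and define how an overlapping addition differs from a switch.
- Use one definition of triple therapy in SAP 7.2.2 (1) and (2), SAP 10.1 item 6 and Protocol 9.2.2.
- Report the number of patients on this mix by arm, whatever is decided. If the omission is intended, say so and give the reason.

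The cost is SAP wording, a matching protocol clarification and a small change to the exposure algorithm. Appendix 3 already holds the drug codes and no new data are needed. The downside is that a few switchers with overlapping supply may be classed as escalations; a sensitivity analysis treating all patients captured only by (d) as switches would show whether this matters.
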